4. ESTIMATED DURATION OF THE STUDY

Three years (1 month preparation, 24 months enrollment, 11 months publication prior to closure)

5. LAY LANGUAGE SUMMARY OR SYNOPSIS (no more than one paragraph)

Following painful surgical procedures of the breast, postoperative analgesia is often provided with a paravertebral nerve block (PVB). For intense, but shorter-duration acute pain, a single-injection of local anesthetic is used with a duration of approximately 12 hours. Recently an alternative block has been reported: the serratus plane block.² The theoretical benefits include ease of administration since it is a plane superficial to the PVB and therefore easier to identify and target with ultrasound (therefore increasing success rate); and an increased safety margin as there are fewer anatomic structures in the immediate area which could be injured with the needle; and, the target plane is much further from the intrathecal/epidural space relative to the PVB, therefore leakage of cerebrospinal fluid or injury to the spinal cord are less likely with the serratus compared to the PVB.³ There are, therefore, multiple theoretical reasons to prefer the serratus over the PVB. Unfortunately, it remains unknown if the analgesia provided by this new technique is comparable to that provided with the PVB.⁴ We therefore propose to compare these two techniques with a randomized, subject-masked, active-controlled, parallel-arm clinical trial.

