7. BACKGROUND AND SIGNIFICANCE

Following painful surgical procedures of the breast, postoperative analgesia is often provided with a

paravertebral nerve block (PVB). For intense, but shorter-duration acute pain, a single-injection of local anesthetic is used with a duration of approximately 12 hours. The PVB has several limitations: it can decrease blood pressure, and very rare—but serious—complications have occurred, including neuraxial injection, neuraxial hematoma, and pleural puncture.¹ An alternative block has been described: the serratus plane block.² The theoretical benefits include ease of administration since it is a plane superficial to the PVB and therefore easier to identify and target with ultrasound (therefore increasing success rate); and an increased safety margin: there are few anatomic structures in the immediate area which could be injured with the needle; and, the target plane is much further from the intrathecal/epidural space relative to the PVB. Lastly, the plane may be easier to catheterize for continuous peripheral nerve blocks relative to the relatively-small volume PVB.³

There are therefore multiple *theoretical* reasons to prefer the serratus plane block. Unfortunately, it remains unknown if the analgesia provided by this new technique is comparable to that provided with the PVB.⁴ We therefore propose to compare these two techniques with a randomized, subject-masked, active-controlled, parallel-arm, human subjects clinical trial.

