9. RESEARCH DESIGN AND METHODS

This investigation will be a randomized, subject-masked, active-controlled parallel-arm, human subjects clinical trial. Of note, we will be using standard-of-care local anesthetic under an FDA-approved purpose and do not plan to research a possible change of indication or use of these medications as part of this research project. The treatments in both groups are currently used at our institution and there is true clinical equipoise at this time. The only difference in treatment between subjects who enroll versus those not enrolled in this study will be those who enroll will have the decision between which anatomic block location determined randomly, as opposed to the physician simply choosing him/herself.

Enrollment. Consenting adults undergoing breast surgery with a planned single-injection regional analgesic will be offered enrollment. Patients undergoing breast surgery with a planned perineural catheter regional analgesic will be excluded. Study inclusion will be proposed to eligible patients prior to surgery. If a patient desires study participation, written, informed consent will be obtained using a current UCSD IRB-approved ICF. Selection for inclusion will not be based on gender, race, or socioeconomic status. The study population of interest includes men and women of all races and socioeconomic status. Inclusion and exclusion criteria are listed in section #9 below.

Preoperative Procedures. Following written, informed consent, we will collect baseline anthropomorphic information (e.g., age, sex, height, and weight). All subjects will have a peripheral intravenous (IV) catheter inserted, standard noninvasive monitors applied, supplemental oxygen administered via a nasal cannula or face mask, and placed in the sitting position. Midazolam and fentanyl (IV) will be titrated for patient comfort, while ensuring that patients remain responsive to verbal cues. Both possible block locations will be viewed with ultrasound. If one or both of the locations is unacceptable for block placement in the clinician's opinion, the subject will not be randomized and will not proceed further with the study.

Subjects will then be randomized using a computer-generated list and opaque, sealed envelopes to

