one of two treatment groups: (blocks of 4, stratified for unilateral vs. bilateral surgery): (1) serratus plane or (2) paravertebral block. All blocks will be placed by a regional anesthesia fellow or resident under the direct supervision and guidance of a regional anesthesia attending (or by the attending themselves).

The area of needle insertion will be cleaned with chlorhexidine gluconate and isopropyl alcohol. All blocks will be placed using standard UCSD ultrasound-guided techniques as previously described.^{2,3}

Ropivacaine 0.5% (20 mL for unilateral surgery; 16 mL each side for bilateral surgery) will be administered via the needle into the target plane(s). For PVBs without axillary involvement, this will be at the T3 and T5 levels. For PVBs with axillary involvement, this will be at the T2 and T4 levels. For unilateral PVBs, 10 mL of local anesthetic will be injected per level. For bilateral PVBs, 8 mL of local anesthetic will be injected per level.

Single-injection blocks will be considered successful if, within 30 minutes, the subject experiences decreased sensation to cold temperature with an alcohol pad over the approximate level of the ipsilateral 4th thoracic dermatome. Misplaced blocks will be replaced successfully, or the patient excluded from further study participation. For subjects undergoing bilateral surgical procedures, a block using the same protocol will be administered on the contralateral side.

Intraoperatively, all subjects will receive a general anesthetic using inhaled and intravenous anesthetic and oxygen. Intravenous fentanyl will be administered for cardiovascular responsiveness to noxious stimuli at the discretion of the anesthesia provider.

Postop: Subjects will be discharged with a prescription for oxycodone 5 mg tablets for supplementary analgesia and instructed to record the time at which they take their first opioid tablet as well as the time at which they believe the block starts to wear off.

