Outcome measurements (end points). Pain scores will be recorded using the NRS. Within the recovery room, pain scores, opioid requirements, and antiemetic administration will be recorded by nursing staff masked to treatment group. The morning following surgery, all subjects will be contacted by phone or in person [if hospitalized] to record lowest, average, highest, and current pain scores; sleep disturbances, and nausea using a 0-10 Likert scale (0 = no nausea; 10 = vomiting). For outpatients, opioid requirements will be recorded while inpatients will have opioid requirements extracted from the electronic medical record. In addition, we will extract antiemetic use from the electronic record. We will collect the times at which subjects felt their block resolve and they consumed their first opioid analgesic pills following recovery room discharge.

Hypothesis 1: Following breast surgery, **analgesia** will be non-inferior in the recovery room with a serratus plane block compared with a paravertebral block as measured with the Numeric Rating Scale.

Hypothesis 2: For breast surgery, **opioid** consumption will be non-inferior in the operating and recovery rooms with a serratus plane block compared with a paravertebral block (primary: cumulative intravenous morphine equivalents).

Primary end point: *In order to claim that serratus plane blocks are non-inferior to paravertebral blocks, both Hypotheses 1 and 2 must be at least non-inferior.*

Statistical methods. Descriptive statistics will be provided by arm and in aggregate. Baseline characteristics of arms will be compared using the Wilcoxon-Mann-Whitney and Fisher's Exact tests. Key characteristics that are significantly different ($p<0.05$) will be included as covariates in the analysis models.

Primary aim. We will test the noninferiority of the serratus nerve block compared to the paravertebral nerve block. The 95% confidence interval (CI) associated with the Wilcoxon-Mann-Whitney test will be derived for the group difference (paravertebral minus serratus) in median pain scores within the recovery room. If the lower limit of the 95% CI is greater than -1.25, we will conclude noninferiority. If there are significant differences between the groups in any key characteristics, these characteristics will be included as covariates in a linear model. The same noninferiority margin (-1.25) will be applied to the 95% CI for the covariate adjusted group difference in mean pain derived from the linear model.

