The noninferiority of the serratus nerve block with regard to total opioid consumption within the operating and recovery rooms will be tested in the same manner as pain, i.e. comparing the limits of a 95% CI associated with the Wilcoxon-Mann-Whitney test to a predefined noninferiority margin (in this case 2 mg). Covariate adjusted linear models will again be applied in the event that key characteristics are significantly different between the groups.

Sample size justification. Power for the Wilcoxon-Mann-Whitney derived noninferiority testing is based on 10,000 simulated trials. We simulated pain scores from a discrete distribution with median (interquartile range) 3 (2-5).⁵ Between the quartiles, the probability of each score was assumed constant. The distribution for each group was assumed to be the same. The sample size of $n=50$ per group provides 82% power to detect noninferiority in pain with a margin of 1.25. Similarly, opioid consumption was assumed to follow a truncated normal distribution with mean 2.5 mg and standard deviation 2 mg, and minimum value 0 mg. The sample size of $n = 50$ per group provides at least 95% power to detect noninferiority with margin 2 mg. Therefore, we will enroll 50 subjects for each of two treatments with primary end point values for a total enrollment of 100 subjects with a primary end point. To allow for dropouts, we request a maximum enrollment of 120 subjects. Noninferiority in pain is tested first, and if significant, noninferiority in opioid consumption is tested. Under this hierarchical testing framework, no adjustment in alpha is necessary to control Type 1 error.⁶

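### Randomised patients whose misplaced block is not successfully replaced are excluded after allocation, and with no analysis set defined both noninferiority comparisons would leave them out

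*Combined protocol and SAP*

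**What the plan says.** The order of events in Section 9 matters.

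- **Before randomisation:** both block sites are viewed with ultrasound, and a patient with an unacceptable site is not randomised. This is the only block-related removal before allocation.
- **Randomisation:** "Subjects will then be randomized using a computer-generated list and opaque, sealed envelopes".
- **After randomisation:** the block is placed. It counts as successful if cold sensation near the fourth thoracic dermatome is reduced within 30 minutes. Then: "Misplaced blocks will be replaced successfully, or the patient excluded from further study participation". The word "misplaced" is not defined or tied to the cold test.
- **Analysis:** the statistical methods name no intention-to-treat, per-protocol or other set, and give no rule for excluded patients. The target is expressed as "we will enroll 50 subjects for each of two treatments with primary end point values", followed by "To allow for dropouts, we request a maximum enrollment of 120 subjects".
- **Reporting:** descriptive statistics by arm are promised, but block failures, replacements and exclusions are not mentioned.

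Section 6 requires noninferiority on both pain and opioid use. Sections 5 and 7 list a higher success rate among the theoretical benefits of serratus; Section 7 calls the plane "therefore easier to identify and target with ultrasound (therefore increasing success rate").

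**The concern.** Placement success is a result of the allocated technique. Removing patients because of it means that, to the extent removals occur, the arms compared are no longer the arms randomised.

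The stated objective is the relative risks and benefits of the two blocks, and success rate is one of the claimed benefits. The exclusion takes out the patients in whom a difference in success would show. Without counts by arm and without an all-randomised analysis, a reader could not tell whether, or in which direction, the exclusions moved the conclusion. Outcome data that are never collected cannot be recovered at the analysis stage.

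**Working it through.** **1. Who is left out.** "Misplaced" can be read in two ways.
- If it includes a failed cold test (the natural reading, though not stated), every unrecovered failure leaves, and the comparisons rest in effect on successful first or replaced blocks.
- If it means wrong position only, a correctly positioned block that fails the cold test stays, and only unreplaced misplaced blocks leave.

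On both readings the removal follows allocation and depends on the technique.

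**2. The plan's own figure.** Inputs from Section 9: pain median 3 (quartiles 2 and 5), same distribution in both arms, margin 1.25, lower limit of the 95% Wilcoxon-Mann-Whitney interval, 50 per arm, stated power 82%. I spread 25% probability over each of scores 0–2, 3, 4–5 and 6–10. Simulation gives 81%, so the figure is reproduced. Other readings of the quartile rule give 74% to 87%. At 60 per arm with no failures, power is about 87%.

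**3. Room for exclusions.** 120 − 100 = 20, and 20/120 = 16.7%. This allowance must also cover other dropouts.

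**4. Illustration.** The failure rates and the penalty are assumptions; the protocol gives neither. 60 are randomised per arm, and pain is equal after successful blocks. An unrecovered failure adds 3 points, capped at 10. The cap costs 1, 2 and 3 points at scores 8, 9 and 10, each with probability 0.05, so the mean penalty is 3 − 0.05 × (1 + 2 + 3) = 2.7. Expected exclusions = 60 × (sum of the two rates). True mean difference = rate difference × 2.7.

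Chance of concluding pain noninferiority:

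| Failure rate, serratus/PVB | Expected exclusions | Exclusions dropped | All randomised | True mean difference (worse arm) |
|---|---|---|---|---|
| 5%/2% | 4.2 | 86% | 82% | 0.08 (serratus) |
| 10%/5% | 9 | 85% | about 78% | 0.14 (serratus) |
| 10%/10% | 12 | 84% | 84% | 0 |
| 2%/5% | 4.2 | 86% | 89% | 0.08 (PVB) |
| 5%/10% | 9 | 85% | 90% | 0.14 (PVB) |
| 20%/5% (extreme) | 15 | 82% | 56% | 0.41 (serratus) |
| 5%/20% (extreme) | 15 | 82% | 96% | 0.41 (PVB) |

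**5. Sample-size part of the gap.** Once failures are dropped, the two arms have identical distributions. The fall from about 87% to between 86% and 82% in the third column is therefore due only to fewer patients. This narrows the gap when serratus fails more and widens it when PVB fails more. With 50 analysed per arm in both versions, the successes-only figure is about 81%. The all-randomised figures are then 69% (10%/5%), 49% (20%/5%), 84% (5%/10%) and 92% (5%/20%).

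**6. What failures alone would need to reach the margin.**
- Mean scale: 1.25/2.7 = 0.46, a rate difference of about 46 points.
- Planned Wilcoxon-Mann-Whitney scale, with no PVB failures: the probability that a PVB score plus 1.25 exceeds a serratus score is 0.661 for a successful serratus block and 0.351 for a failed one. Setting the mixture to 0.5 gives (0.661 − 0.5)/(0.661 − 0.351) = 0.52, about 52 points.

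**7. Opioid.** Using the plan's truncated normal (2.5 mg, SD 2 mg) and margin of 2 mg, a failure penalty of 3 mg leaves the chance at 99–100% in both analyses. With 5 mg at 20%/5% it is 100% against 91%. The joint claim is therefore affected mainly through pain.

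**The case against.** The strongest case against has four parts.

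- **Failures may be few.** Both sites are screened by ultrasound, an attending supervises or places every block, and a misplaced block may be replaced. Only unrecovered failures leave, and nothing in the protocol shows that they are more than trivial. This stands as a limit on the likely size. However, Section 8 reports no pilot data, and if failures are few, keeping them costs almost nothing.
- **Working blocks are a legitimate target.** A successful-block comparison is a recognised choice in noninferiority work, where an all-randomised result may be blurred by whatever care follows a failure. This supports showing that analysis alongside. It does not support leaving the choice unstated, or collecting no data for the other analysis.
- **The wording is not explicit.** Exclusion from further participation is not literally exclusion from analysis, and a reader might infer too readily that only successful blocks will be analysed. That holds fully only if "misplaced" covers a failed cold test. The narrower statement holds on either reading: no endpoint collection is planned for excluded patients and no analysis set brings them back.
- **The expected direction is conservative.** A reader might infer that the exclusion tilts the trial toward serratus. The documents do not support that: Sections 5 and 7 expect serratus to succeed more often, so the exclusion would work against the noninferiority claim. That expectation is called theoretical, and the opposite direction cannot be ruled out.

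**Conclusion.** The concern holds in this form: a post-randomisation exclusion that depends on the performance of the allocated block, combined with no defined analysis set, leaves these patients out of both required comparisons. It should be fixed.

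The size and direction of any bias are unknown. Under the assumed 3-point penalty, modest differences in failure rate (3 to 5 percentage points) move the chance of concluding pain noninferiority by about 3 to 7 points. Only extreme differences move it by 14 to 26 points, and part of each gap is sample size.

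A reader might infer that the exclusion could manufacture a false claim of noninferiority. These scenarios do not show that: the true mean difference is at most 0.41 against a margin of 1.25, and failures alone would need rates about 46 to 52 points apart. What shifts is the chance of the conclusion, and the reader's ability to judge it. The stated 82% power is not in question.

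**What to change.** - Replace exclusion from the study with continued collection of recovery-room pain and operating- and recovery-room opioid data on every randomised patient who has surgery.
- Define the primary analysis set as all randomised patients by allocated arm, for both endpoints, and state that this analysis decides noninferiority.
- Present the successful-block (per-protocol) analysis alongside as supporting, and discuss any disagreement.
- Define "misplaced" and say whether it includes a failed cold test.
- Report block failures, replacements and exclusions by arm.

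The clinical handling of a failed block is unchanged.

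**Cost:** protocol and analysis wording, plus data capture for the affected patients. In the recovery room, "pain scores, opioid requirements, and antiemetic administration will be recorded by nursing staff masked to treatment group", so that part is already routine. Operating-room opioid must also be captured for these patients, since "Intravenous fentanyl will be administered for cardiovascular responsiveness to noxious stimuli at the discretion of the anesthesia provider". The data will be slightly more variable. If serratus blocks do fail more often, the chance of concluding noninferiority falls, for example from 86% to 82% at 5%/2% under the assumptions above.

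### Does the pain margin of 1.25 mean two different things in the Wilcoxon analysis and in the linear-model fallback, so that the 82% power misleads?

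*Combined protocol and SAP*

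**What the plan says.** All of this is in section 9 (Research Design and Methods) of the combined protocol and SAP.

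- **Default rule** (Primary aim). The 95% interval associated with the Wilcoxon-Mann-Whitney test is formed for paravertebral minus serratus. "If the lower limit of the 95% CI is greater than -1.25, we will conclude noninferiority".
- **Fallback** (Primary aim). "If there are significant differences between the groups in any key characteristics, these characteristics will be included as covariates in a linear model". Then: "The same noninferiority margin (-1.25) will be applied to the 95% CI for the covariate adjusted group difference in mean pain".
- **Power** (Sample size justification). "Power for the Wilcoxon-Mann-Whitney derived noninferiority testing is based on 10,000 simulated trials". The simulated score is discrete, with median 3 and quartiles 2 and 5, and the arms are identical. "Between the quartiles, the probability of each score was assumed constant". With 50 patients, this "per group provides 82% power to detect noninferiority in pain with a margin of 1.25". No power is given for the linear model.
- **Measurement** (Outcome measurements). In the recovery room, "pain scores, opioid requirements, and antiemetic administration will be recorded by nursing staff masked to treatment group". The section does not say which score, or which summary of several scores, represents a patient.

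**The concern.** The power model gives a probability to each discrete score, which suggests one whole-number score per patient. All pairwise differences between arms are then whole numbers, and so is the Wilcoxon limit. Exceeding -1.25 is the same decision as being -1 or higher, and any margin strictly between 1 and 2 gives the same answer. A difference in means is not restricted in this way, so there 1.25 really is 1.25. One written margin therefore acts as a looser rule in the default analysis and a tighter one in the fallback, and a chance baseline p<0.05 decides which applies.

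Pain is the gatekeeper: opioid consumption is tested only if pain passes, and both must pass. If the fallback had power in the 60s while readers believed 82%, the trial would be weaker than it claims. Measured on the mean, the Wilcoxon rule would also pass a true worsening of 1.25 more often than the nominal one-sided 2.5%.

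**Working it through.** **Inputs from the plan.** n = 50 per arm; two-sided 95% interval (one-sided 2.5%); margin 1.25; discrete score with median 3 and quartiles 2 and 5; no true difference.

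**Assumed, because the plan gives no tails.** 25% spread evenly over 0-2, 25% at 3, 25% over 4-5, 25% over 6-10.
- Mean = (0+1+2)/12 + 3(0.25) + (4+5)(0.125) + (6+7+8+9+10)(0.05) = 0.25 + 0.75 + 1.125 + 2.0 = 4.125.
- Mean square = 5/12 + 9(0.25) + 41(0.125) + 330(0.05) = 24.29.
- SD = √(24.29 − 4.125²) = 2.70.

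**1. The plan's own figure.** The lower Wilcoxon limit is roughly the k-th smallest of the 50 × 50 pairwise differences, with k = n²/2 − 1.96·√(n²(2n+1)/12) = 1250 − 1.96 × 145.1 ≈ 966. Simulated power is 80.7% from this order statistic (100,000 trials) and 81.7% from R's wilcox.test (10,000 trials). The stated 82% is reproduced.

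**2. Steps in the limit.** In all 10,000 wilcox.test trials the limit lay within 0.0001 of a whole number. Power was the same 81.7% at margins 1.01, 1.25, 1.50 and 1.99.

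**3. The mean-difference rule on the same data.** SE = 2.70 × √(2/50) = 0.54. Power ≈ Φ(1.25/0.54 − 1.96) = Φ(0.355) ≈ 64%; simulation gives 63.0%. The two rules disagree in 18.0% of trials, nearly always with only Wilcoxon passing.

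**4. The fallback when it is triggered.** These figures keep only trials in which one covariate is imbalanced at p<0.05.

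| Covariate R² with pain | Fallback power |
|---|---|
| 0 | 61% |
| 0.10 | 65% |
| 0.20 | 70% |
| 0.40 | 81% |

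The tails matter too. Among 597 score allocations with the stated quartiles and Wilcoxon power of 80-84%, the unadjusted mean rule ranged from 59% to 82%.

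**5. Weighting by how often the fallback is used.** The plan does not list the key characteristics; section 9 names age, sex, height and weight as examples of baseline data. With k independent characteristics the trigger probability is 1 − 0.95^k. As a rough check, overall power ≈ 81% − trigger × (81% − fallback power), taking fallback power as 61% to 70%. The last column is a simulation of the whole procedure (8,000 null trials per setting, independent normal covariates, R² 0 or 0.20).

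| k | Trigger | Rough loss (points) | Simulated overall power |
|---|---|---|---|
| 1 | 5% | 0.6-1.0 | 80-81% |
| 3 | 14% | 1.6-2.9 | about 78-79% |
| 4 | 19% | 2.0-3.7 | about 77-78% |
| 6 | 26-27% | 2.9-5.3 | about 76% |

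**6. Error rate.** Seven patterns with a mean worsening of exactly 1.25 were tried. The Wilcoxon rule passed in 4.3-7.5% of trials and the mean interval in 2.3-2.4%. In all seven the median pairwise difference is -1, which is inside the margin on the Wilcoxon scale. Where that parameter reaches -2, the Wilcoxon rule passes in at most 2.5%. The excess exists only if the Wilcoxon rule is judged on the mean, which is not the quantity it estimates.

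**7. Finer per-patient scores.** Half-points, continuous scores or a mean of several scores give Wilcoxon power of 61-76%, or 80% in one version with a shorter top tail. The ordering can then reverse: continuous scores up to 8 gave Wilcoxon 80% and mean rule 83%.

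**The case for a change.** The strongest case for a change is that the plan calls the two margins the same although they behave differently, and that this is built into whole-number data whatever the tails. The analysis route depends on chance imbalance in a list of characteristics that is neither given nor limited. The per-patient score is undefined, and if it were a finer summary the 82% would be too high in most scenarios tried. Putting this right would need only wording and a rerun of the simulation.

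Much of that stands as description. The two margins are on different scales, and one sentence naming the recovery-room score would help a reader. None of it alters a decision:

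- Restating the rule as a limit of -1 or higher leaves every Wilcoxon conclusion on whole-number scores unchanged.
- Attaching the 82% to the Wilcoxon test is what the sample-size paragraph already does.
- Quoting power only for the default analysis, and not for a contingent adjusted model, is a defensible choice.
- Writing in an effective margin on the mean of about 1.4-1.5 would fix a number that rests on assumed tails and seven assumed shift patterns.
- The plan already shows the change of scale: it speaks of medians for the Wilcoxon analysis and of means for the linear model.

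The undefined score is a gap that the plan's own power model points to filling with a single whole-number score, and on that reading the 82% is correct. A finer score would lower the planning figure in most scenarios tried, but the interval and the conclusion drawn from it would remain valid.

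**Conclusion.** No change to the plan follows. The observation is correct: on whole-number scores the Wilcoxon rule cannot distinguish 1.25 from any other margin strictly between 1 and 2, and the mean-difference rule at 1.25 is stricter (about 63% against 81% under the base tails). The consequence is small. The stated 82% is right for the analysis it names. Error is not inflated on the Wilcoxon parameter, and a switch to the fallback makes noninferiority harder to claim under these tails. Allowing for how seldom the fallback is used, the cost is about 0 to 4 points of power for one to four key characteristics and about 5 for six.

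These sizes rest on assumed tails, one whole-number score per patient, independent normal covariates with R² of 0 or 0.20, and an assumed number of key characteristics. Finer scores could narrow or reverse the contrast between the rules. What is left is missing detail that the analysts can supply in the report: which recovery-room score was used, and that the two analyses work on different scales.

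### A chance baseline p<0.05 on unlisted characteristics brings in a second noninferiority analysis; the plan does not say which one decides, and only the Wilcoxon interval was powered

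*Combined protocol and SAP*

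**What the plan says.** All the relevant text is in Section 9, Research Design and Methods.

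- **Baseline comparison (Statistical methods).** "Baseline characteristics of arms will be compared using the Wilcoxon-Mann-Whitney and Fisher's Exact tests". Key characteristics that differ at p<0.05 "will be included as covariates in the analysis models". They are not listed or defined. The Preoperative Procedures paragraph gives age, sex, height and weight only as examples of baseline data.
- **Pain (Primary aim).** The 95% interval associated with the WMW test is derived for paravertebral minus serratus: "If the lower limit of the 95% CI is greater than -1.25, we will conclude noninferiority". Then: "If there are significant differences between the groups in any key characteristics, these characteristics will be included as covariates in a linear model". And: "The same noninferiority margin (-1.25) will be applied to the 95% CI for the covariate adjusted group difference in mean pain".
- **Opioids.** The method is the same, with a 2 mg margin: "Covariate adjusted linear models will again be applied in the event that key characteristics are significantly different between the groups".
- **Power (Sample size justification).** "Power for the Wilcoxon-Mann-Whitney derived noninferiority testing is based on 10,000 simulated trials". With 50 per group this "provides 82% power to detect noninferiority in pain with a margin of 1.25". No power is given for a linear model.
- **Randomization.** Blocks of 4, stratified by unilateral or bilateral surgery. The statistical methods do not name this factor as a covariate.

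**The concern.** There are three problems.

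1. **The trigger carries no useful information.** Randomization makes a baseline p<0.05 a chance event, apart from any effect of exclusions after randomization. It says nothing about whether the variable predicts pain. It also cannot select the one factor on which the design balances the arms.
2. **Precedence is not settled.** The wording on inclusion in the analysis models suggests that the linear model takes over. But the sentence that concludes noninferiority from the WMW interval is unconditional. With no list of characteristics, what counts as key could be decided after the data are seen.
3. **The two analyses measure different things against one margin.** The WMW interval concerns a location shift, and the linear model a difference in means. The same data can pass one and fail the other.

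This bears on the main claim of the trial. Both endpoints must pass, and opioids are tested only if pain passes. A chance imbalance, in height for example, could decide which method gives the verdict. If the model replaces WMW, the 82% does not describe the planned procedure.

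**Working it through.** **Inputs from the plan.** 50 per arm; identical arms; pain scores discrete with median 3 and quartiles 2 and 5, with constant probability between quartiles; margin 1.25; two-sided 95% intervals; trigger p<0.05.

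**Assumptions, because the plan is silent.** The number of characteristics (main case: four, independent, non-prognostic) and the tails of the pain distribution. One quarter of the probability is placed on each of 0-2, 3, 4-5 and an upper group: 6-10 (layout A, SD 2.70) or 6-9 (layout B, SD 2.48).

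**Step 1: reproduce the stated power.** WMW power, from the order-statistic interval on pairwise differences over 40,000 simulated trials, is 80.6% (A) and 83.2% (B). These bracket the stated 82%. Inverting the tie-corrected test instead changes power by at most 0.3 points.

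**Step 2: the linear model on the same data.** Approximate power is Φ(1.25 / (SD·√(2/50)) − 1.96).
- A: Φ(1.25/0.540 − 1.96) = Φ(0.36), about 64%. Simulated: 63.1%.
- B: Φ(1.25/0.497 − 1.96) = Φ(0.56), about 71%. Simulated: 70.0%.

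**Step 3: how often the trigger fires.** For four independent tests, 1 − 0.95⁴ = 18.5%. Simulated: 18.7% (A) and 18.4% (B).

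**Step 4: the rule as a whole, main case.**

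| | A | B |
|---|---|---|
| Linear power in triggered trials | 61.2% | 67.8% |
| Triggered trials: WMW passes, linear fails | 20.3% | 15.9% |
| Triggered trials: linear passes, WMW fails | 0.2% | 0.3% |
| Overall power if linear replaces WMW | 76.8% | 80.3% |
| Overall power if both must pass | 76.8% | 80.3% |
| Overall power if either may pass | 80.6% | 83.3% |

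The loss under replacement is 80.6 − 76.8 = 3.8 points (A) or 83.2 − 80.3 = 2.9 points (B). As a check on A, 18.7% × (20.3% − 0.2%) = 3.8 points. The verdicts conflict in 3.8% (A) or 3.0% (B) of all trials.

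**Step 5: vary the assumptions (loss under replacement).**
- Two characteristics: trigger about 10%, loss 1.4-1.8 points.
- Eight characteristics: trigger 33-34%, loss 5.2-6.9.
- Age, height, weight and sex, with height-weight correlation 0.4 and 2% men: trigger 14%, loss 2.1-2.8.
- One of four characteristics explaining about 10-30% of the variance: loss 1.5-3.3.
- Five other layouts of the pain scores: WMW 73-87%, linear in every trial 57-77%, loss 2.1-4.1.

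**Step 6: opioids.** With a normal distribution with parameters 2.5 and 2 truncated at 0, and a 2 mg margin, both methods exceed 99.9% power.

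**Step 7: the stratification factor.** Blocks of 4 hold the arm difference within a stratum to at most 2. The most extreme case, 2/50 against 0/50, gives Fisher p = 0.49. Before exclusions the trigger therefore cannot fire on this factor.

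**Step 8: the scales differ.** Pairwise differences of whole-number scores are whole numbers, so the WMW limit clears -1.25 exactly when it is -1 or higher. In layout A, WMW power is about 81% for any margin from 1.01 to 1.99, while linear power runs from 45% to 96%. If serratus scores are shifted by 1 point in 75% of patients and 2 points in 25% (an assumed mean shift of 1.25), WMW passes about 8% of trials and the linear model about 2%.

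**The case against.** The strongest reply is that the effect is small and lies on the safe side. The linear model almost never rescues a trial that WMW fails (0.2-0.3% of triggered trials), so the switch costs power rather than credibility. The loss arises only if the model replaces WMW or both must pass. For the four variables the protocol names, it is 2-3 points, less than the uncertainty from the unknown pain tails. The word key may also be meant to limit the candidates to prognostic variables. All of this stands as to size. None of it supplies the missing list or the missing precedence rule.

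Three further points stand as caveats:

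- Patients whose misplaced block is not replaced successfully are excluded after randomization. Imbalance in the analysed set could therefore be partly systematic. A baseline p-value is still a poor guide to what to adjust for.
- Relying on WMW alone is slightly more lenient on the mean scale than the switching rule: about 8% against about 7% passes under the assumed 1.25 shift. On whole-number scores, its -1.25 acts as any margin between 1 and 2.
- The 120 maximum includes dropouts, and the target with a primary endpoint is 100. A linear primary analysis is therefore costlier than a comparison with 120 suggests.

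Covariate adjustment is good practice when the covariates are fixed in advance. The objection here is to the trigger, not to adjustment.

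**Conclusion.** The concern holds. The plan lets a chance event, on characteristics it does not list, bring in a second analysis with a different target and the same margin. It does not state which analysis decides. Under the replacement reading, which the wording suggests, the stated 82% overstates pain power by about 3-4 points in the main case, and by 1.4-6.9 points for two to eight independent non-prognostic characteristics. Where the trigger fires, power is 61-68% in the main case, and roughly one such trial in five or six gets a verdict that depends on the method. If WMW governs, or either may pass, there is no loss. These sizes rest on the assumed number of characteristics and tail layout. Opioid power is not materially affected, and no general claim about type 1 error is made. This should be corrected before the analysis, but it does not threaten the trial.

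**What to change.** Delete the baseline-test trigger for both endpoints and name one deciding analysis per endpoint now. Suggested wording: *The WMW 95% CI alone decides noninferiority for pain and for opioids, whatever the baseline comparison shows.* Add a linear model with covariates named in advance (the unilateral/bilateral stratum plus, for example, age and weight), labelled as a sensitivity analysis that does not decide noninferiority.

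This changes wording only, needs no new data and keeps the powered method. Its price is a deciding analysis that is unadjusted, leaves out the stratification factor and tests a location shift rather than a mean difference, with the leniency on the mean scale noted above.

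If the sponsor prefers the prespecified linear model as primary, pain power and sample size must be restated. At 50 per arm with non-prognostic covariates, power is about 63% (A) or 69% (B). With one covariate explaining 10%, 20% or 30% of the variance it is about 66%, 73% or 79% (A) and 74%, 79% or 85% (B). With non-prognostic covariates, 80% power needs about 2 × (SD × 2.80/1.25)² = 74 (A) or 62 (B) per arm; simulation at those sizes gives 79.1% and 79.4%. That is 148 or 124 patients with a primary endpoint, against the planned 100, before any allowance for dropouts.
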